15.11.3	Procedures for Termination or Suspension	63
16.	References	64
17.	Appendices	70
18.	Version History	70

1. Glossary

Term	Definition
ADE	Adverse Device Effect
AE	Adverse Event
ASADE	Anticipated Serious Adverse Device Effect
BIPP	Bismuth iodoform paraffin paste
CEC	Clinical Event Committee
CFR	Code of Federal Regulation
CIP	Clinical Investigation Plan
CRO	Clinical Research Organization
CRS	Chronic rhinosinusitis
CRF	Case Report Form
CTA	Clinical Trial Agreement
CV	Curriculum Vitae
DD	Device Deficiency
DMC	Data Monitoring Committee
DoH	Declaration of Helsinki
DTL	Delegated Task List
eCRF	Electronic Case Report Form
EC/IRB/REB/Ethics Board	Ethics Committee
ENT	Ear, nose, and throat
ESS	Endoscopic sinus surgery
FAL	Foreseeable Adverse Event List

Medtronic Business Restricted

Novapak Clinical Investigation Plan

MDT22031

Version A

Page 7 of 73

Medtronic

Term	Definition
FD	Financial Disclosure
FDA	Food and Drug Administration
FDAAA	Food and Drug Administration Amendments Act
FEDS	Functional endoscopic dilation sinus surgery
FESS	Functional endoscopic sinus surgery
GCP	Good Clinical Practice
HCL	Hydrochloric acid
HIPAA	Health Insurance Portability and Accountability Act
IB	Investigator Brochure
IC	Informed Consent
ICH	International Conference of Harmonization
IRB	Institutional Review Board
IFU	Instructions For Use
MDD	Medical Device Directive
MedDRA	Medical Dictionary for Regulatory Activities
MHLW	Ministry of Health, Labour, and Welfare
MN	Minnesota
MW	Molecular weight
NP	Nasal polyposis or Nasal polyps
NSR	Non-Significant Risk
OR	Operating room
PETG	Polyethylene terephthalate glycol
PHI	Protected Health Information

Medtronic Business Restricted

Novapak Clinical Investigation Plan

MDT22031

Version A

Page 8 of 73

Medtronic

Term	Definition
QoL	Quality of Life
RA	Regulatory Authority
REB	Research Ethics Board
SADE	Serious Adverse Device Effect
SAE	Serious Adverse Event
SAP	Statistical Analysis Plan
SBS	Solid Bleached Sulfate
SC	Steering Committee
SNOT-22	Sino-Nasal Outcome Test-22
SR	Significant Risk
SID	Subject Identification
UAE	Unavoidable Adverse Event
US	United States
USP Grade	United States Pharmacopeial Convention Standard

Device Trademarks

Novapak™ is a trademark of Medtronic Xomed, Jacksonville, FL, USA.

Medtronic Business Restricted

2. Synopsis

Title	Novapak Prospective Observational Clinical Trial
Clinical Study Type	Prospective, Observational, Case-Series, Post-Market, Clinical Trial
Product Name	Novapak Nasal Sinus Packing and Stent CS3600 and CS3900
Sponsor	Medtronic ENT [name] All funding for this study will be the responsibility of this sponsor.
Local Sponsor	Medtronic Canada ULC [name] Canada [name]
Indication under investigation	
The Novapak Nasal Sinus Packing and Stent is intended for use in patients undergoing nasal/sinus surgery as a space-occupying stent to:
 
• Separate tissue or structures compromised by surgical trauma.• Separate and prevent adhesions between mucosal surfaces in the nasal cavity.• Control minimal bleeding following surgery or trauma by tamponade effect, blood absorption, and platelet aggregation.• Act as an adjunct to aid in the natural healing process. 
Novapak Nasal Sinus Packing and Stent is indicated for use as a nasal packing to treat epistaxis.
 
This study will be conducted in accordance with these indications.

Investigation Purpose	Obtain clinical data on the safety and effectiveness of the Novapak device under use as intended in the device indications.
Product Status	This study will be conducted in geographies where the Novapak device is commercially released.
Primary Objective(s) and/or Endpoint(s)	
The primary objective is to assess the safety of the Novapak Nasal Sinus Packing and Stent device used as indicated post-operatively in patients undergoing nasal/sinus surgery by:
 
• Collecting all AEs directly attributed to the device and/or those that cannot be determined; and calculating a point estimate and confidence interval• Collecting all AEs and calculating an overall rate and safety profile for the device
Secondary Objective(s) and/or Endpoint(s)	The secondary objectives are to confirm device effectiveness during the procedure, 2 weeks and 1-month post treatment.

Medtronic Business Restricted

Novapak Clinical Investigation Plan

MDT22031

Version A

Page 10 of 73

Medtronic

Study Design	Prospective, observational, multi-site, non-controlled, non-randomized, case-series, with a 2 week and 1-month follow-up in adults undergoing nasal/sinus surgery with Novapak Nasal Sinus Packing and Stent device used as indicated post-operatively		
Sample Size	This study will include a minimum of 75 subjects.		
Inclusion/Exclusion Criteria	
Inclusion Criteria
 
 1. Subject is at least 18 years of age. 2. Subject undergoing nasal/sinus surgery with the intended need for nasal sinus packing (i.e., Novapak). 3. After being informed of the nature of the study; the subject understands, agrees to its provisions, is willing to participate and provide written consent. 4. Mentally stable and able to follow the instructions for self-assessment/questionnaire completion. 
Exclusion Criteria
 
 1. Subject has a shellfish allergy. 2. Subject has known bleeding disorder or prescribed anticoagulants. 3. Subject has craniofacial abnormalities that may interfere with access to the sinuses. 4. Subject is immunocompromised (e.g., taking immunosuppressive medication). 5. Subject is participating in another investigational device, biologic, or drug study and has not completed the primary endpoint(s) or if there is a potential for clinical interference beyond the primary endpoint. 		
Study Procedures and Assessments	Visit	Procedure	Data Collection
	Pre-Surgery	Inform subject about the study requirements Ask shellfish allergy questions Schedule surgery	Consent document signed SNOT-22 (subject)
	Surgical Procedure (Day 0)	Endoscopic exam Functional Endoscopic Sinus Surgery Other interventions if bleeding more than minimal	Lund- Mackay Scores Lund-Kennedy Scores (baseline) Procedural Details Boezaart Surgical Field Grading Scale ⁷⁷ (pre-packing) Boezaart Surgical Field Grading Scale ⁷⁷ (post-packing)

Medtronic Business Restricted

			Collect Adverse Events and/or device deficiencies Question: Bleeding controlled post packing?
	Day 1, 2, 3...	Daily Irrigations	Subject records volume / date Subject records any Adverse Events
	Day 14 (-2, +5)	Office Visit Endoscopic exam Observe for residual product (remove) Debride Adhesions (if necessary) Review Subject Irrigations Records	SNOT-22 (subject) Lund-Kennedy Scores Question: residual product? Score Adhesions (Valentine method ⁴⁴) Question: Bleeding controlled? Collect Adverse Events and/or device deficiencies
	Day 30 (-2, +12)	Office Visit Endoscopic exam Debride Adhesions (if necessary)	SNOT-22 (subject) Lund-Kennedy Scores Score Adhesions (Valentine method ⁴⁴) Collect Adverse Events and/or device deficiencies
Safety Assessments	Collect all AE observations and characterize those that are device related.		
Statistics	
 1. All continuous variables summarized as the number of subjects, means, standard deviations, medians, minimums, maximums, and interquartile ranges. 2. Categorical variables will be summarized as frequencies and percentages. 3. Analyses of the primary and secondary endpoints will be descriptive. 		

3. Introduction

3.1 Background

Chronic rhinosinusitis (CRS) affects millions of people each year,^{1,2} a condition defined as symptoms lasting for more than 12 weeks without complete resolution and with or without nasal polyps. Symptoms include inflammation of the nose and the paranasal sinuses with either nasal discharge or nasal blockage, obstruction, or congestion, with or without facial pain and/or pressure with or without reduction or loss of smell.³ In most cases, medical management is sufficient to relieve the symptoms, and if that should fail, surgical procedures are well-established. Approximately 250,000 sinus procedures are performed each year in the US to relieve acute rhinosinusitis (ARS) or CRS, most commonly known as functional endoscopic sinus surgery (FESS).¹⁻³

Dressing and packing devices in the ear, nose, and throat (ENT) and other procedures such as FESS are commonly used to absorb fluids during or after surgery, to improve and maintain hemostasis, to allow wounds to heal postoperatively, and/or when local measures have proven unsuccessful in controlling minor or severe epistaxis (bleeding). Dressings and packing products are some of the most common products used in surgeries. These types of dressing and packing products are placed in the affected area by physicians until sufficient pressure exists to tamponade the bleeding.⁴⁻¹¹ The use of chitosan as a packing material has revealed several favorable biological properties (i.e., biocompatibility, biodegradability, low toxicity, and mucoadhesiveness), thus making this polymer a promising substrate for biomaterial medical devices. The general safety of chitosan has been found quite satisfactory in recent review articles.¹¹⁻²³

Other efficacious and well-tolerated options are gauze, synthetic sponge packs, and balloon packing, which are the most conservative approaches to controlling any kind of bleeding. Some products such as gauze or sponges can be coated with an antibiotic or a product such as bismuth iodoform paraffin paste (BIPP) to prevent infection.^{8-10,24-26} Variances in the devices (i.e. size, shape, attachment of a string) have been made to allow for convenient access to certain parts of the anatomy. For example, standard gauze or sponges are used to treat bleeding in the anterior nasal area; however, epistaxis originating in the posterior nasal source would indicate the need for long ties attached to the gauze pack or sponges for easy removal. An alternative device to posterior packing is a balloon catheter which can be inserted into the nasopharynx via the nostrils and inflated with sterile water.^{27,28} Over time, the balloon deflates and the volume drops, therefore it can remain in the cavity for up to 72 hours. Most gauze and sponges used in patients with CRS or other procedures are removed within 48 hours, depending on the extent of the bleeding.^{5,6,24,29,30}

No consensus has been established about nasal splint or nasal packing choices and intranasal stay of nasal splints after surgery.³¹ Researchers have observed no difference in pain and the perception of nasal fullness or complications such as synechia, infection, hematoma, or perforations when nasal splints remained in place for 3, 5, or 7 days.³¹⁻³³ Some data have suggested superior performance of

Medtronic Business Restricted

bioabsorbable (dissolvable) packs compared with non-absorbable packs with respect to patient comfort. For hemostasis and wound healing, variation in performance metrics makes interstudy comparison difficult.³⁴⁻³⁶ Weber (2001 and 2009) and Zhao (2013) confirm that <3 days of intranasal stay of nasal packing is non-influential on the surgical outcome and non-functional for prevention of adhesions.^{32,33,37} In order for wound healing to take place, a minimum of 5 to 7 days and up to 2 weeks with appropriate changing of dressing is recommended in other studies.³⁸⁻⁴⁰

Medtronic Xomed has developed a nasal sinus stenting / packing material for use in post-sinus surgery, including ESS. Many new biomaterials have been developed to control hemostasis, reduce adhesion formation, and improve healing. Several biomaterials are used for post-surgical nasal packing in the field of otorhinolaryngology including those that contain chitosan.⁴¹⁻⁴⁴ Chitosan is a kind of natural polysaccharide that is widely exploited for biomedical applications due to its good biocompatibility, low immunogenicity and specific biological activities.⁴⁵ Chitosan is derived from the shells of crustaceans (e.g., crab, shrimp), and has demonstrated biocompatibility and high biodegradability, including being easily excreted in the urine.^{12,14,21,42,43,45-47} Used for post-surgical nasal packing in the field of otorhinolaryngology, chitosan has been developed to control hemostasis and reduce adhesion formation and improve healing.^{12,15-18,20-22,41-43} Chitosan-based in situ gelling systems have already gained much attention as smart biomaterials in the development of several biomedical applications, such as for drug delivery systems and regeneration medicine.^{14,21,23,45,48}

Products made from chitosan have shown good hemostatic control and improved healing in animal and human studies.^{28,41,42,44,49-54} Absorbable dressings for ENT surgery made with chitosan are Hemopore® Hemostatic Bioresorbable Nasal Dressing (Stryker Neuro Spine ENT, Kalamazoo, MI, USA), PosiSep™ and PosiSep™ X Intranasal Splints (Hemostasis, LLC, Saint Paul, MN, USA), and XeroGel® (Entellus Medical™, Plymouth, MN, USA). Other non-chitosan-derived absorbable nasal dressings are MeroGel® Nasal Dressing and Sinus Stent (Anika Therapeutics, Inc., Bedford, MA, USA; Medtronic Xomed, Jacksonville, FL, USA), MeroPak® Bioresorbable Nasal Packing and Sinus Stent (Medtronic Xomed, Jacksonville, FL, USA), Nasastent® (Arthrocare Corporation, Austin, TX, USA), Surgicel® Original Absorbable Hemostat, Ethicon US, LLC, a J&J company, Cincinnati, OH, USA), Oxycel (Woundcare, Worcester, England), Stammberger Sinu-Foam® (Arthrocare ENT Corporation, Austin, TX, USA and Remscheid, Germany) Surgi shield (D. med, Seoul, South Korea), and NasoPore® (Stryker Neuro Spine ENT, Kalamazoo, MI, USA). It is important to note that in the literature, the term absorbable has been typically used interchangeably with the term dissolvable though most of these dressings do not absorb into local tissue.

3.2 Purpose

Medtronic, Inc. is sponsoring the Novapak Nasal Sinus Packing and Stent Study, a prospective, observational, multi-site, non-controlled, non-randomized, case-series, investigational, clinical study. The purpose of this study is to assess the safety of the Novapak Nasal Sinus Packing and Stent device

Medtronic Business Restricted

used as indicated post-operatively in patients undergoing nasal/sinus surgery. In addition, this study will observe some key measures of device effectiveness from the physician and subject perspective.

The Novapak Nasal Sinus Packing and Stent study is being conducted as a non-significant risk post-market investigational study in the US and Canada in accordance with Canadian local regulations and ISO 14155:2020 in support of EU MDR regulatory submission for a CE Mark.

4. Objectives and/or Endpoints

4.1 Objectives

The study is being conducted to support the safety profile of the Novapak Nasal Sinus Packing and Stent device used as indicated post-operatively in patients undergoing nasal/sinus surgery.

4.1.1 Primary Objective(s)

The primary objectives of this study are to assess the safety profile of the Novapak Nasal Sinus Packing and Stent device used as indicated post-operatively in patients undergoing nasal/sinus surgery.

4.1.1.1 Primary Study Endpoint(s)

The study endpoints for safety will be:

- 1) the statistical analysis of designated primary safety endpoint AEs that are directly attributable to the device and/or for which direct cause cannot be determined
- 2) the rate of all AEs as defined below. Refer to **Section 13** for more details regarding endpoint analysis. The data resulting from this study will be summarized in a final report generated by the Study Sponsor.

4.1.1.1.1 Primary Device Safety Endpoints

The primary safety endpoint is an assessment of all AEs that are directly attributable to the device and/or for which cause cannot be determined, and that meet the definition of designated primary safety endpoint AEs (see section 11.4) that will be used to determine the point estimate and its confidence interval. This endpoint will be analyzed by calculating the point estimate with a confidence interval of its rate. All AEs will be collected for each subject from time of treatment until their study completion.

Study completion for each subject is the time point at which the 30-day follow-up visit is completed, outstanding AE follow-up (if any) has been concluded, and a Study Exit CRF has been completed. For subjects who withdrew or were lost to follow-up, study completion will be the date of withdrawal or the date the subject meets the definition of lost to follow-up. Refer to **Section 13** for how missing data will be handled.

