11.5.2 Adverse Event and Device Deficiency Reporting Requirements

Regulatory reporting of AEs and DDs will be recorded and reported according to local regulatory requirements. It is the responsibility of the Investigator and the sponsor to abide by the AE reporting requirements stipulated by local law and the study site's IRB/REB.

Sponsor shall fully record all of the following: (a) any adverse event of a type identified in the CIP as being critical to the evaluation of the results of that clinical investigation, (b) any serious adverse event, (c) any device deficiency that might have led to a serious adverse event if appropriate action had not been taken, intervention had not occurred, or circumstances had been less fortunate, (d) any new findings related to any event referred to in previous points and (e) any additional CIP procedure relatedness.

All reporting shall include the date of the adverse event, treatment, resolution, assessment of seriousness and the relationship to the investigational device and the related procedure.

Medtronic Business Restricted

Table 11: AE and DD Reporting Requirements

SAEs	
Investigator shall submit to:	
Medtronic	All geographies: Report to the sponsor, without unjustified delay, all serious adverse events.
RA	All geographies: Submit to RA per local reporting requirement.
IRB/REB	All geographies: Submit to IRB/REB per local reporting requirement.
Sponsor shall submit to:	
RA	All geographies: Submit to RA per local reporting requirement.
IRB/REB	All geographies: Submit to IRB/REB per local reporting requirement.
ADEs	
Investigator shall submit to:	
Medtronic	All geographies: Submit in a timely manner after the investigator first learns of the effect.
RA	All geographies: Submit to RA per local reporting requirement.
IRB/REB	All geographies: Submit to IRB/REB per local reporting requirement.
Sponsor shall submit to:	
RA	All geographies: Submit to RA per local reporting requirement.
IRB/REB	All geographies: Submit to IRB/REB per local reporting requirement.
SADEs	
Investigator shall submit to:	
Medtronic	All geographies: Immediately after the investigator learns of the event or of new information in relation to an already reported event.
RA	All geographies: Submit to RA per local reporting requirement
IRB/REB	All geographies: Submit to IRB/REB per local reporting requirement.
Sponsor shall submit to:	
RA	All geographies: Submit to RA per local reporting requirement.

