13.3 Primary Objective(s)

The primary objective is to assess the safety of the Novapak Sinus Packing and Stent device for use in patients undergoing nasal/sinus surgery:

- Collect all AEs directly attributed to the device and/or those that cannot be determined
- Collect all AEs and establish an overall rate and safety profile for the device

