### 7.2 General Methodology

Categorical variables will be summarized with frequencies and percentages.

Summaries of continuous variables will include the sample size, mean and standard deviation. Additional summaries of the number with missing data, minimum, median, maximum, or sum may be presented as appropriate.

Statistical inferences will be performed as needed. For continuous variables, t-test, ANOVA, or nonparametric Wilcoxon test will be used; for categorical variables, Chi-square test or Fisher's exact test will be used.

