## 7.9 Evaluation of Objectives

### 7.9.1 Safety objective assessment

The safety objective is evaluated by:

- The number of Adverse Events that are directly attributed to the device and/or those that cannot be determined.
- The number of Adverse Events.

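### The primary safety result is stated inconsistently: an undefined AE filter, a promised rate and interval that the SAP does not specify, and an analysis population without treated but ineligible subjects

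*Protocol*

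**What the plan says.** **Which events count.** Protocol 4.1.1.1 names as its first safety endpoint "the statistical analysis of designated primary safety endpoint AEs that are directly attributable to the device" or whose direct cause cannot be determined. Protocol 4.1.1.1.1 adds to relatedness the condition "that meet the definition of designated primary safety endpoint AEs (see section 11.4"). The synopsis and protocol 13.3 carry no such condition; the latter reads "Collect all AEs directly attributed to the device and/or those that cannot be determined". SAP 7.9.1 likewise has "The number of Adverse Events that are directly attributed to the device and/or those that cannot be determined".

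**What is reported.** Protocol 4.1.1.1.1 states: "This endpoint will be analyzed by calculating the point estimate with a confidence interval of its rate". The synopsis also commits to collecting these events "and calculating a point estimate and confidence interval". Protocol 4.1.1.1 refers to section 13 for details of the analysis, but 13.3 speaks only of collecting events and, for all AEs, an overall rate. The SAP measure is a number of events. The nearest general rule is in SAP 7.2: "Categorical variables will be summarized with frequencies and percentages".

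**Who is analysed.** SAP 7.1.3 defines one population: patients who meet the eligibility criteria and in whom the device was used. Protocol 9.17.1 says that all data up to a subject's exit will be used, and lists failure to meet the criteria among the reasons for exit.

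**Relatedness.** Under Table 10 (protocol 11.5.1), investigator and sponsor each rate relatedness as not related, possible, probable or causal. Table 9 puts cases that cannot be assessed into *possible*, together with weak relationships.

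**The concern.** In a single-arm descriptive study, the estimate and its interval are the whole primary result. A reader should be able to tell from the plan which events enter the numerator, what the denominator is, who is included and how the interval is computed. Here the protocol contains two definitions of the endpoint, one of which cannot be applied because its defining list does not exist. The document meant to specify the analysis stops at a count.

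The population rule matters separately. Excluding treated subjects who turn out to be ineligible removes their device exposure and any device AE they had. Such cases are foreseen: protocol 9.16 gives unmet eligibility criteria as an example of a deviation. Protocol 3.2 says the study supports a CE Mark submission, so the safety estimate will be read by people who were not involved in the study.

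**Working it through.** **1. Is there a definition?** Table 9 in section 11.4 covers AE, adverse device effect, device deficiency, the relatedness and relationship categories, SAE, SADE, serious health threat and unavoidable AE. It has no entry for designated or primary-endpoint AEs, and no other section supplies one. The section runs to its end without a redaction mark. The term cannot simply mean device-related, because 4.1.1.1.1 adds it to relatedness.

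**2. Can the promised rate be computed from the plan?** The plan has no figure of its own to reproduce: the minimum of 75 is stated not to come from statistical methods (protocol 13.5, SAP 6), and no confidence level or expected rate is given. The counts below are therefore assumptions, with 75 treated subjects.

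Exact (Clopper-Pearson) limits for x of n at level 1 − α:

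- lower = Beta quantile at α/2 with parameters (x, n − x + 1)
- upper = Beta quantile at 1 − α/2 with parameters (x + 1, n − x)
- for x = 0, lower = 0 and upper = 1 − (α/2)^(1/n)

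*Unit.* Take 6 events in 3 of 75 subjects. As an event rate this is 6/75 = 8.0 per 100 subjects (exact Poisson 95% CI 2.94 to 17.41). As a proportion of subjects it is 3/75 = 4.0% (exact 95% CI 0.83 to 11.25%).

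*Interval for 3/75 = 4.0%:*

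| Choice | Lower | Upper |
|---|---|---|
| Wald 95%: 0.04 ± 1.96 × √(0.04 × 0.96/75) | −0.43% | 8.43% |
| Exact 90% | 1.10% | 10.01% |
| Exact 95% | 0.83% | 11.25% |

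**3. What does the population rule do?** Suppose one treated subject with a device AE is found ineligible (exact 95% CIs).

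| Subjects with a device AE | Kept (n = 75) | Dropped (n = 74) |
|---|---|---|
| 1 | 1/75 = 1.33% (0.03 to 7.21%) | 0/74 = 0% (0 to 4.86%) |
| 3 | 3/75 = 4.00% (0.83 to 11.25%) | 2/74 = 2.70% (0.33 to 9.42%) |

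The zero case checks by hand: 1 − 0.025^(1/74) = 4.86%.

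**4. What does the relatedness cut do?** If 8 subjects have an AE rated possible, probable or causal, and 3 of them one rated probable or causal, the rate is 8/75 = 10.67% (4.72 to 19.94%) or 3/75 = 4.00% (0.83 to 11.25%).

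**The case against.** The strongest reply is that little can go wrong in practice. The study has no hypothesis and no threshold (protocol 13.1, 13.5). All AEs are tabulated whatever the primary definition (protocol 4.1.1.1.2, SAP 7.9.1). SAP 3 says that the protocol provides the guidelines for the SAP and that an addendum may cover further analyses, and protocol 13.1 requires departures from the statistical plan to be justified in the report. The promised interval is therefore not cancelled, only unspecified.

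Much of this stands, and it rules out several stronger readings:

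- A reader might infer that the sponsor could pick the designated events after seeing the data. The documents do not support this. SAP 3 says that a reported objective is analysed as the SAP describes, and SAP 7.9.1 has no filter, so the unfiltered endpoint is the likely one. The defect is an orphan reference that leaves two definitions in the protocol.
- A reader might infer that the SAP has no unit at all. It implies events, and protocol 11.1 has each event reported separately. What is missing is a denominator and an interval.
- A reader might infer that relatedness is left wholly open, or in the sponsor's hands. Table 9 gives undetermined cases a natural place in *possible*, and the investigator also rates. What remains open is whether weak but assessed *possible* cases count, and whose rating governs.
- A reader might infer that a subject of unknown shellfish-allergy status, whom protocol 9.4 allows to be included, would be reclassified as ineligible after a reaction and dropped. No section provides for that, so the example above does not depend on the reason for ineligibility.

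The reply does not answer the population point. Tabulating all AEs does not bring back a subject whom SAP 7.1.3 has removed, because the SAP has no other population. Protocol 13.1 does not settle it either: it defines the study population as eligible consenting patients, yet says that data from all enrolled subjects will be used as appropriate.

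**Conclusion.** The point holds as an inconsistency that should be fixed. The protocol restricts the primary safety endpoint by a term it never defines, while its own synopsis, section 13.3 and the SAP apply no restriction. The promised rate and interval have no denominator, level or method in protocol section 13 or the SAP. SAP 7.1.3 would leave out device AEs in treated but ineligible subjects, against protocol 9.17.1.

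The size depends on counts that the documents do not give. With 75 treated subjects assumed, dropping one affected subject lowers the exact 95% upper limit from 7.2% to 4.9% when that subject has the only event. The choice between events and subjects can double the figure (8.0 per 100 against 4.0%). These changes concern the reported estimate and its interval; no test decision depends on them.

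**What to change.** - **Protocol 4.1.1.1 and 4.1.1.1.1:** delete the word *designated* and the reference to 11.4, so that the endpoint matches the synopsis, 13.3 and SAP 7.9.1.
- **SAP 7.1.3:** add a safety set of all subjects in whom the device was used, regardless of eligibility, and use it for all safety analyses.
- **Protocol 13.3 and SAP 7.9.1:** report the proportion of that set with at least one qualifying device AE, with an exact (Clopper-Pearson) two-sided 95% confidence interval. Keep the SAP's event count alongside.
- **Both documents:** state which relatedness levels qualify and whose rating is used, with the alternative cut and the alternative rater as sensitivity analyses. The choice is the sponsor's. Including *possible* captures the cases that cannot be assessed but also counts weak relationships.

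The cost is wording in two documents. No new data are needed, since Table 10 already has both parties rate relatedness. There are two consequences to accept. The headline changes from the SAP's event count to a per-subject proportion. If *possible* is included, the rate will be the same or higher, as in the assumed 10.7% against 4.0%.
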